# 8 STATISTICAL METHODS

A formal statistical analysis plan (SAP) that will provide details of all analyses and presentation of registry data will be approved prior to database lock and data analysis.

Descriptive statistics will comprise the number of observations (n), mean, standard deviation (SD), median, minimum, and maximum for continuous variables; and n and percent for categorical variables, with the number of patients who do not have missing values as the denominator.

For this registry, no imputation for missing data will be performed. Analyses will be conducted using observed cases.

# 8.1 Sample Size

Up to 1000 patients are anticipated. No pre-specified statistical hypotheses will be tested, therefore no formal power calculations were performed. Instead, the precision of 95% confidence intervals around key response variables was estimated. Note that the number and size of analysis groups will be determined by the treatments selected by the patients in this sample; therefore, group sizes may not be identical.

Table 1 below provides 2-sided 95% confidence interval (CI) around an expected response rate of 67.5% for CR-SMFRS score in patients treated with ATX-101 during Phase 3 clinical trials, where response was defined as an improvement of at least one grade.

Table 1 Precision and 95% Confidence Intervals for Various Sample Sizes, Based on an Expected Patient Response Rate of 67.5%

Sample size (N) 250	95% CI 61.7, 73.3	500	63.4, 71.6
750	64.1, 70.9		

Table 2 below provides the 2-sided 95% CI around expected levels of patient satisfaction rates. 13

Table 2 Precision and 95% Confidence Intervals for Various Combinations of Sample Size and Patient Satisfaction Rates

	Probable Rates of Patient-reported Satisfaction				
_	80%	85%	90%		
Sample Size (N)	95% CI	95% CI	95% CI		
250	75.0, 85.0	80.6, 89.4	86.3, 93.7		
500	76.5, 83.5	81.9, 88.1	87.4, 92.6		
750	77.1, 82.9	82.4, 87.6	87.9, 92.1		

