Number of Patients	Approximately 1000 patients will be recruited from approximately 100 sites in the US and Canada.
Study Procedures	Details of the physician's practice setting will be recorded once for each site; treatment logistics will be recorded at the first treatment session for each patient.  Patients considering treatment for improvement of SM fullness due to SMF will be recruited. Eligible patients will be enrolled in the registry and data will be collected from patients who elect treatment until their SMF reduction treatment is completed or discontinued. Patients who do not initially elect treatment will be followed to determine whether or not they subsequently undergo treatment, and if not, until up to one year has elapsed since enrollment and no treatment has been elected. Physicians will treat and assess patients according to their discretion.  At enrollment, data on previous relevant SMF and facial aesthetic treatment(s) will be collected from the patients, and as necessary, their medical records, along with baseline SMF assessments and information on treatment goals. Demography (birth date, sex, race, ethnic origin), Clinical Information (height, weight, lifestyle habits), and a brief medical history (including diabetes, cardiovascular disease) will be collected, Information including treatment received for SMF reduction, treatment procedures and outcomes, follow-up assessments of SMF, and adverse events (AEs) will be recorded at subsequent clinic visits or telephone contacts (Data for Collection). Patient medical history data will be updated, as appropriate, at the first treatment visit.
Data Collection Procedures	Electronic data capture (EDC) will be used for participating sites to record clinical data, data questionnaires and assessment data via electronic case report forms (eCRFs) accessed through a secure internet portal. Data entry screens will be designed to efficiently capture the desired data elements from patient medical records (Data for Collection).
Data Elements	Physician Practice Profile At each site, the physician will complete the Physician Practice Setting Questionnaire, including the following information:  • Physician characteristics:  - Clinical history / specialty, including board certification  - Years of aesthetic practice  - Percent of practice focused on facial aesthetics  - Physician approach to discussing new treatment options  - Number and roles of physicians and other healthcare providers (HCPs) in the

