# 8.2.2.1 Main Efficacy Endpoint: Submental Fat (SMF) Assessments

The following SMF assessments (Appendix 11) are planned at each visit:

- Clinician-Reported Submental Fat Rating Scale (CR-SMFRS) score
- Patient-Reported Submental Fat Rating Scale (PR-SMFRS) score
- Patient-Reported Submental Fat Impact Scale (PR-SMFIS) score
- Submental Skin Laxity Grade (SMSLG)
- Subject Self Rating Scale (SSRS)
- Patient Self-Perception of Age (SPA) scale
- Patient Global Questions

Overall and individual component summaries for each scale, where applicable, will be provided using descriptive statistics at each timepoint. Changes from baseline will be summarized descriptively for each treatment cohort at each post-baseline assessment. Exploratory analysis of covariance (ANCOVA) methods will also be used to assess change from baseline at the end-of-treatment follow-up timepoint, where treatment type and baseline score will be included in the model. The ANCOVA results will be generated in SAS using PROC MIXED. Cochran-Mantel-Haenszel (CMH) tests for association, stratified by site, will be used to assess the responses.

For CR-SMFRS and PR-SMFRS assessments, the number and percent of patients in each treatment cohort who are responders, ie, have at least a 1-grade improvement, will be presented, along with the corresponding 95% CI. Responses to the other SMF assessments will be summarized similarly.

For the SSRS, a subject is defined as a responder for the assessment if the response was positive relative to the score's neutral response option (ie, "slightly satisfied," "somewhat satisfied," or "extremely satisfied" where neutral is "neither satisfied nor dissatisfied").

An SMSLG responder at an assessment time is defined as a subject who stayed the same SMSLG score or had improvement in SMSLG score relative to baseline. This scale is different from the others in that "no change" is counted as a responder. The reason for this distinction is

that the intent is not to investigate whether ATX-101 reduces/improves skin laxity, but rather to investigate whether ATX-101 is associated with an undesirable increase in skin laxity. Accordingly, the categories are, effectively, skin laxity either "did not increase" or "did increase."

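### Tables 1 and 2 assume independent patients without saying so, and the exploratory ANCOVA has no site term although the CMH test on the same scales is stratified by site

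*Protocol*

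**What the plan says.** **Precision.** Section 8.1 states that no hypotheses are pre-specified and no power was calculated; instead, "the precision of 95% confidence intervals around key response variables was estimated". Table 1 is built on an "expected response rate of 67.5% for CR-SMFRS score in patients treated with ATX-101" in Phase 3, for cohorts of 250, 500 and 750. Table 2 has the same three cohort sizes for "Probable Rates of Patient-reported Satisfaction" of 80%, 85% and 90%. Section 8.1 does not mention site, design effect or ICC.

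**Sites.** The synopsis says "Approximately 1000 patients will be recruited from approximately 100 sites in the US and Canada", an average of about 10 per site. Under Section 3.1 the participating physician prescribes according to usual practice. Under Appendix 11.2 the investigator scores CR-SMFRS from clinical examination.

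**Analysis.** Section 8.2.2.1 and the synopsis describe an exploratory ANCOVA of change from baseline, run in PROC MIXED, "where treatment type and baseline score will be included in the model". No site term or random effect is named. The next sentence of Section 8.2.2.1 says "Cochran-Mantel-Haenszel (CMH) tests for association, stratified by site, will be used to assess the responses". Responder percentages are to be shown with 95% CIs, for which no method is given.

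**The concern.** Patients at one site share a treating team, a technique and, for CR-SMFRS, a rater. Their outcomes may therefore be correlated, and a correlated sample carries less information than the same number of independent patients. The protocol expects practice and provider to matter: Section 9.8.2 says so, and the CMH test is stratified by site.

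Two things are then at stake. First, the tables in Section 8.1 would promise more precision than the registry can deliver. The synopsis also points to that section when it calls a cohort of 250 well powered, so readers may rely on it. Second, two analyses of the same scales treat site differently with no reason given. The CMH test compares treatments within sites only, whereas the ANCOVA as written pools within-site and between-site differences and attaches a standard error that assumes independent patients.

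The source of correlation differs between the tables. Shared scoring applies to Table 1 only. Table 2 is patient-reported, so correlation there can come only from the shared treater and practice.

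**Working it through.** **Step 1: reproduce the tables.** Inputs from Section 8.1: p = 0.675 (Table 1) or 0.80, 0.85, 0.90 (Table 2); N = 250, 500, 750; two-sided 95%, z = 1.96. Formula: p ± 1.96·√(p(1−p)/N).

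- 67.5%, N=250: 1.96·√(0.675·0.325/250) = 5.81 points, giving 61.7-73.3 (stated 61.7-73.3).
- 67.5%, N=500: 4.11 points, giving 63.4-71.6 (stated 63.4-71.6).
- 67.5%, N=750: 3.35 points, giving 64.1-70.9 (stated 64.1-70.9).
- 80%, N=250: 4.96 points, giving 75.0-85.0 (stated 75.0-85.0).

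The other eight entries of Table 2 also match to one decimal. The tables therefore contain no allowance for site.

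**Step 2: add a design effect.** Assumptions, none of them in the documents: ICC 0.02, 0.05 or 0.10; equal site sizes; each cohort spread over all 100 sites, so m = N/100. Formulas: DE = 1 + (m−1)·ICC; half-width = 1.96·√(p(1−p)·DE/N); true coverage of the stated interval = 2Φ(1.96/√DE) − 1. For p = 67.5%:

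| N (stated CI) | m | ICC | DE | Effective N | 95% CI | Coverage of stated CI |
|---|---|---|---|---|---|---|
| 250 (61.7-73.3) | 2.5 | 0.02 | 1.03 | 243 | 61.6-73.4 | 94.7% |
| | | 0.05 | 1.075 | 233 | 61.5-73.5 | 94.1% |
| | | 0.10 | 1.15 | 217 | 61.3-73.7 | 93.2% |
| 500 (63.4-71.6) | 5 | 0.02 | 1.08 | 463 | 63.2-71.8 | 94.1% |
| | | 0.05 | 1.20 | 417 | 63.0-72.0 | 92.6% |
| | | 0.10 | 1.40 | 357 | 62.6-72.4 | 90.2% |
| 750 (64.1-70.9) | 7.5 | 0.02 | 1.13 | 664 | 63.9-71.1 | 93.5% |
| | | 0.05 | 1.325 | 566 | 63.6-71.4 | 91.1% |
| | | 0.10 | 1.65 | 455 | 63.2-71.8 | 87.3% |

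**Step 3: a concentrated cohort.** If 250 patients came from about 25 sites with 10 each, DE = 1 + 9·ICC = 1.45 (ICC 0.05) or 1.90 (ICC 0.10). The interval becomes 60.5-74.5 or 59.5-75.5. Uneven site sizes also widen it.

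**Step 4: ANCOVA without a site term.** The direction of the error depends on how treatment is distributed over sites. Here the ICC is that of the ANCOVA residual, which need not equal that of the binary response.

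- *Treatment constant within site, 10 per site.* Type I error = 2(1 − Φ(1.96/√(1+9·ICC))): 7.1%, 10.4% and 15.5% at ICC 0.02, 0.05 and 0.10.
- *Treatments balanced within every site.* Type I error is approximately 2(1 − Φ(1.96/√(1−ICC))): 4.8%, 4.4% and 3.9%, so the test is conservative.

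A null simulation of 100 sites with 10 patients each (model with treatment and baseline only; 1,500 runs per setting) agrees within simulation error. At ICC 0.05 and 0.10 it gave 11.4% and 15.6% with treatment mainly between sites, 6.7% and 11.4% with a mixed pattern, and 4.2% and 3.2% with within-site balance.

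**The case against.** The strongest reply is that this is detail for the SAP. The protocol defers details of all analyses to the SAP. It says which terms the ANCOVA will include, not that no others may be added, and PROC MIXED can take a random site effect. Section 9.8.2 also states an intent to adjust for practice and provider characteristics. The registry has no pre-specified hypothesis, its tests are called exploratory, and no precision target or stopping rule uses the tables.

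Part of this stands. The method for the planned responder-rate CIs is open, so a reader who infers that those intervals will ignore site goes beyond the text. The exploratory status limits the consequence. What does not fall away is what the protocol prints: 12 intervals with an unstated independence assumption, and an ANCOVA whose terms, procedure and software are named without site beside a CMH test that has it. Adjusting for measured practice characteristics does not replace a site variance component.

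Three stronger readings are tempting and not supported:

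- *All ANCOVA p-values will be too small.* This holds only where treatment type follows site. The documents make that plausible, since physicians prescribe by usual practice, but do not establish it. The practice questionnaire expects clinics to report several options with relative frequencies.
- *Clinician scoring undermines both tables.* Table 2 is patient-reported.
- *Coverage of the stated intervals falls to about 82%.* That needs N=750, ICC 0.10 and a site-size coefficient of variation of 0.8 together: DE = 1 + (1.64·7.5 − 1)·0.10 = 2.13. The documents give neither of the last two.

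**Conclusion.** The point holds as a minor one. It is certain that Tables 1 and 2 are independent-patient intervals and that the ANCOVA as described has no site term while the CMH test does. The size of the effect cannot be fixed from the documents, because every figure beyond Step 1 rests on an assumed ICC.

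With ICC 0.02 to 0.10 and even spread over 100 sites, the half-width in Table 1 grows by about 0.1 to 0.4 points at N=250 and 0.2 to 1.0 points at N=750. It grows more if sites are uneven or a cohort sits in fewer sites. The ANCOVA error rate may be too high or too low, depending on how treatments fall across sites, and a site term is the remedy in either case. No stated decision or recruitment target would change.

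**What to change.** 1. In Section 8.2.2.1 and the synopsis, add site as a random effect to the PROC MIXED ANCOVA, so that both analyses recognise site. A random intercept still uses some between-site information, so its results need not coincide with those of the within-site CMH test.
2. State that 95% CIs for cohort response rates use site-clustered variance.
3. In Section 8.1, label Tables 1 and 2 as assuming independent patients, or restate them for a range of assumed ICCs (for example 0.02, 0.05 and 0.10) with the assumed number of patients per site.

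The cost is one model statement, one variance option and a table note or extra columns. Visits, data collection and recruitment do not change. The downside is slightly wider intervals than those now shown.

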# 8.2 Study Populations and Analyses

# **8.2.1** Study Populations

Efficacy and safety analyses will be based upon all enrolled patients who had at least one post-baseline visit, whether or not they elected to received treatment. Additional groups also may be examined, as deemed appropriate, and will be defined in the SAP (eg, sex, initial assessment scores, prior treatments received).

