#### **Adverse Events**

To be collected only for patients who elect treatment for SMF reduction. The following information will be recorded in the Electronic Data Capture (EDC) system:

- Frequency, severity, duration, medication or other treatment required, and outcome of adverse events (AEs) during and after each SMF reduction treatment session:
  - At each visit, patients will have treatment areas examined and be interviewed in an open-ended manner to solicit reports of AEs since the last visit.
  - Patient calls to clinic with post-treatment concerns or symptoms that meet the definition of AEs (eg, pain, swelling, bruising, numbness, induration) will be included in the AE record.

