Statistical Methods	A formal statistical analysis plan (SAP) that will provide details of all analyses and presentation of registry data will be approved prior to data analysis.
	Descriptive statistics will comprise the number of observations (n), mean, standard deviation (SD), median, minimum, and maximum for continuous variables; and n and percent for categorical variables, with the number of patients who do not have missing values as the denominator.
	No imputation for missing data will be performed. Analyses will be conducted using observed cases.
Sample Size	Up to 1,000 patients are anticipated. The number and size of analysis groups will be determined by the treatments selected by the patients in this sample; therefore, group sizes may not be identical. In general, if the sample size in a treatment cohort is at least 250, this study is well-powered to observe an improvement of at least one grade in the CR-SMFRS (Section 8.1)
Analysis Populations	Analyses will be based upon all patients who were enrolled and have at least one post-baseline visit. Additional subgroups also may be examined, as deemed appropriate (eg, sex, initial assessment scores, prior treatments received).
Practice, Patient, and Treatment Data	Data will be summarized, by type of SMF reduction treatment, with descriptive statistics, and presented in listings.
Outcome Data	SMF Assessments
	Results for SMF assessments will be summarized with descriptive statistics at each time point. Changes from baseline will be summarized descriptively for each

CONFIDENTIAL

gistry Study Protocol

treatment cohort at each post-baseline assessment. Exploratory analysis of covariance (ANCOVA) methods will also be used to assess change from baseline at the end-of-treatment follow-up timepoint, where treatment type and baseline score will be included in the model. The ANCOVA results will be generated in SAS using PROC MIXED. Cochran-Mantel-Haenszel (CMH) tests for association, stratified by site, will be used to assess categorical responses. The qualification for a "responder" for each SMF assessment will be further defined in the SAP. For the CR-SMFRS and PR-SMFRS assessments, the number and percent of patients in each treatment cohort who have at least a 1-grade improvement will be presented, along with the corresponding 95% confidence interval (CI). Responses to the other SMF assessments will be summarized similarly.

Protocol ATX-101-15-40M

Amendment 2: 20 Oct 2015

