#### **5.1.2** Baseline Treatment Visit

Information about the patient's treatment procedures, any AEs, and treatment outcomes will be recorded at the first treatment session(s) for each treatment selected for all patients who elect treatment for SMF reduction (treated patients) (Section 5.3.2). The number of and time between treatment visits will vary with the treatment type and specific needs of the patient.

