#### **Adverse Events:**

- Frequency, severity, duration, medication or other treatment required, and outcome of AEs during and after each SMF reduction treatment session
  - At the Baseline visit, patients will have treatment areas examined and be interviewed in an open-ended manner to solicit reports of AEs since the last visit.
  - Patient calls to clinic with post-treatment concerns /symptoms that meet the definition of AEs (eg, pain, swelling, bruising, numbness) will be included in the AE record.

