#### 6 ADVERSE EVENT DEFINITIONS AND REPORTING

#### 6.1 Definitions

#### **6.2** Adverse Event

An adverse event (AE) is any undesirable medical occurrence or worsening of an existing condition that occurs after SMF reduction treatment, irrespective of whether the event is considered treatment related. Abnormal laboratory values should not be reported as AEs; however, any clinical consequences of an abnormality must be reported as such. Safety reporting of non-serious (AEs) and /or serious adverse events (SAEs) will only be done for patients who elect treatment for SMF reduction.

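### The single analysis set requires a post-baseline visit, which is the wrong condition for safety and for the treatment-election rate, and 'baseline' has two meanings

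*Protocol*

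**What the plan says.** **The set.** Protocol Section 8.2.1: "Efficacy and safety analyses will be based upon all enrolled patients who had at least one post-baseline visit, whether or not they elected" treatment. The Analysis Populations row of the synopsis is broader and does not limit itself to efficacy and safety: "Analyses will be based upon all patients who were enrolled and have at least one post-baseline visit". Section 8.2.1 leaves further groups to the SAP, but its examples are subgroups (sex, initial scores, prior treatments), not a separate safety set.

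**Who can contribute an adverse event.** Section 6.2: "Safety reporting of non-serious (AEs) and /or serious adverse events (SAEs) will only be done for patients who elect treatment for SMF reduction". The synopsis agrees: "To be collected only for patients who elect treatment for SMF reduction". Events are recorded from the first treatment session onward (Sections 5.1.2 and 5.3.2). Telephone reports also count, since the synopsis brings into the record "Patient calls to clinic with post-treatment concerns or symptoms that meet the definition of AEs".

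**What 'baseline' means.** Sections 3.1 and 5.3.1 use it for the SMF scores taken at Enrollment. The Data for Collection table gives Enrollment (all patients) and Baseline (treated patients) separate columns, and Sections 5.1.2 and 5.1.3 call the first treatment session the Baseline Treatment Visit. No definition settles which meaning applies in Section 8.2.1.

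**What is at issue.** Section 2 names both the choice of treatment among eligible patients and the safety profile as components of the primary objective.

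**The concern.** A safety denominator should be the patients exposed to treatment, and an election denominator should be the patients who faced the choice. Membership of either group is known without a return visit. Making it depend on one selects on something that happens after exposure or after the choice.

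For safety, a patient who has a bad first session and stays away is the one most likely to be lost. For election, choosing treatment generates a further visit, whereas declining it generates one only if the patient comes back. Which problem arises depends on a word the protocol does not define.

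**Working it through.** **The plan's own figures.** The only computable figures in Section 8 are the intervals in Tables 1 and 2. They follow p ± 1.96·√(p(1−p)/n). For p = 0.675 and n = 250: √(0.675 × 0.325/250) = 0.0296, half-width 5.8 points, interval 61.7 to 73.3, as printed. All 12 intervals reproduce to 0.1 point. They take n as given, so the choice of analysis set does not affect them.

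**Inputs.** The documents give up to 1000 enrolled patients (Section 8.1). They give no treated share, adverse event rate or non-return rate. Every such value below is assumed, for illustration only.

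**Reading A: baseline is the first treatment session.** This also covers enrollment and first treatment on one day.
- A patient treated once who does not come back has no later visit. Section 3.1 lists clinic visits and telephone contacts as different things, so a call does not clearly qualify as a visit. The patient leaves the safety set with any event already recorded.
- The rule in Section 8 that percentages use patients with non-missing values does not restore someone already excluded.
- Assume 500 patients in one treatment column and 350 with an event (70%). If 5% (25) are dropped and all had an event: (350 − 25)/(500 − 25) = 325/475 = 68.4%. If 10% (50) are dropped: 300/450 = 66.7%. If those dropped have the average event rate, the figure stays at 70%.
- Assume an uncommon event in 10 of 500 (2.0%), with 5 of the 10 among those dropped: 5/475 = 1.05% or 5/450 = 1.11%. The rate is roughly halved.
- Election: treated and untreated non-returners can both be dropped, so the direction depends on which group fails to return more often. With 600 of 1000 electing and 20% non-return in both groups: 480/(480 + 320) = 60%, no bias. When baseline is literally the first session, untreated patients also have no such visit, so the criterion is not properly defined for them.

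**Reading B: baseline is Enrollment and treatment follows on a later day.**
- The first treatment session is itself a post-baseline visit. Every treated patient is retained and the safety denominators by treatment are right.
- An untreated patient qualifies only by returning. With 600 of 1000 electing (true rate 60%) and a fraction u of the other 400 not returning, the reported rate is 600/(600 + 400(1 − u)).
- u = 0.2: 600/920 = 65.2%. u = 0.4: 600/840 = 71.4%.

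**Untreated patients in the safety set.** They cannot contribute an event. Assume 525 of 750 treated patients have one (70%). Adding 250 untreated patients to a pooled denominator gives 525/1000 = 52.5%. Section 8.2.2.3 tabulates events by treatment type, where untreated patients have no column, so this affects no planned table.

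**The case against.** The strongest reply is that the planned tables escape most of the harm.

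- A reader might infer that including untreated patients dilutes the adverse event rates. It does not. Sections 8.2.2 and 8.2.2.3 report by treatment type, and no pooled event rate or untreated comparator is specified. This part of the reply stands in full.
- A reader might infer that untreated patients distort the efficacy results. They have no post-baseline SMF score (Section 5.3.4), and Section 8.2.2.1 summarises observed cases within treatment cohorts. Their inclusion has no effect. This also stands.
- Reading B can be argued to be the more natural one. Change from baseline uses the Enrollment scores, and a set that covers untreated patients makes sense only if they have a baseline. On that reading treated patients are kept, apart from those enrolled and treated on one day who never return; their number is unknown. This limits the safety problem but does not remove it, because the visit schedule itself names the first session Baseline.
- Section 8.2.1 covers only efficacy and safety, so the election rate is reached only through the broader synopsis sentence, and no election denominator is stated elsewhere. Untreated patients also have follow-up of up to one year and are asked for final assessments (Sections 3.1 and 9.8.4). Both are fair. They bear on how likely and how large the bias is, but the two statements of the analysis set still differ in scope.
- A reader might infer that the election rate is inflated whichever meaning of baseline applies. That is too strong, as the equal non-return example shows.
- The registry is descriptive, and the SAP, which is not at hand, could add detail. What Section 8.2.1 hands to it is additional groups, so the main set remains as written here.

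**Conclusion.** The concern holds in a limited form. The post-baseline-visit condition is wrong for safety and for election, and each meaning of baseline exposes one of the two. Under the first-session meaning, or with same-day enrollment and treatment, treated non-returners and their recorded events leave the safety set. Under the Enrollment meaning with later treatment, the election rate is biased upward if the synopsis wording is applied and some untreated patients do not return.

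The figures above show direction and plausible scale under assumed inputs. They are not estimates for this registry. The point should be fixed because it concerns two named parts of the primary objective and costs little. It is not a must-fix, since the documents do not show that the planned by-treatment tables will be wrong.

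**What to change.** Amend Section 8.2.1 and the Analysis Populations row of the synopsis together, so that they agree, and carry the wording into the SAP.

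1. Define 'baseline' once, and use a different term for the first treatment session.
2. Safety set: all patients with at least one SMF reduction treatment session, regardless of any later visit, with telephone-reported events included.
3. Enrolled set: all enrolled eligible patients, for patient characteristics and the election rate.
4. Outcome set: keep the post-baseline condition only here, for change-from-baseline outcomes in treated patients.

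The cost is wording only; no additional data are needed. The one downside is that the reported election rate may be less favourable.
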